10 APPENDIX: ALGORITHM TO COMPUTE PRIMARY OUTCOME

The primary outcome is oxygen-free days at study day 28. It can take values -1, 0, 2, ..., 27, 28. When computing oxygen free days, the “outcome” for each participant should be a length 30 vector of zeros and ones that indicate which of the 30 possible values (-1, 0, 2, ..., 27, 28) that OFDs could take for that participant. This representation allows for arbitrary censoring of the outcome. For example [0,1,1,0,0,...,0] indicates that OFDs could be either 0 or 1. If there is loss-to-follow-up, withdrawal, or missing follow-up information, there can be interval censoring. The algorithm below is designed to compute OFDs in this representation.

- If participant was deceased by study day 28, OFDs is [1,0,0,0,0,...,0]
- For study day 1 through 28, compute whether or not supplemental oxygen was used (code with “yes” or “no”), or if supplemental oxygen use was uncertain (code with “?”).
 - For our purposes supplemental oxygen means oxygen use that exceeds any pre-enrollment home oxygen use. Home oxygen use is recorded in the “Medical History” form in variables mhco2, mhio2, and the amount (L/m) in field home_ox. If a participant had not used pre-enrollment home oxygen, then it should be assumed that all hospital and post-discharge use of oxygen counts against oxygen-free days. If a participant had used pre-enrollment home oxygen, then only the supplemental oxygen use that exceeds the amount used at home should count against oxygen-free days. If the participant is in the inpatient phase of the study and using standard supplemental oxygen (o2type = “O2 by mask or nasal prongs”), then the L/m recorded on the vitals signs form (o2_lpm_cannula_sofa) must exceed the amount used at home (home_ox). If hospital oxygen use takes any other value except “No O2 therapy” and “O2 by mask or nasal prongs”, then that study day should count against oxygen free-days.
 - If the participant is in the outpatient phase of the study (i.e., after discharge from the enrollment admission or after 28 days, whichever comes first), but is not hospitalized, then only the post-discharge home oxygen use that exceeds the amount used at home prior to enrollment (if any) will count against oxygen-free days. The phone script and outpatient form are designed to record only the home oxygen use that exceeds any pre-hospitalization oxygen use.
 - If the participant is in the outpatient phase of the study, but is hospitalized, the branching logic on the outpatient form determines whether the participant had used oxygen. Any hospital oxygen use during the outpatient phase counts against oxygen-free days.
 - If the preceding calculations cannot be made for any particular study day, then the supplemental oxygen status is “?” for that study day.
- The preceding step results in “yes”, “no”, or “?” for each study day 1 through 28.
 - If there are no “?” values, then OFDs is 28 minus the number of days between and including the days of the first “yes” and the last “yes”.
 - If there are “?” before the first “yes” or after the last yes, then OFDs is partially observed and multiple values are possible. To compute the possible values, consider each possible pair of first ‘yes’ and last ‘yes’ days, and compute the associated OFDs.

OFDs should be represented as a vector of length 30, one element for each value that OFDs can take: -1, 0, 1, ..., 27, 28. There should be a 1 for each element that OFD that is possible for this participant, and a zero otherwise. The -1 (first) element should take a value 0 if the participant was known to be alive at day 28 and 1 otherwise.

11 APPENDIX: CUMULATIVE LOGIT MODEL

11.1 Model Formulation

The cumulative logit model can be written in terms of the covariates X and an ordinal outcome variable G , where probabilities of outcome value g or smaller are modeled as follows

$$\Pr(G \leq g | X) = \text{expit}(\alpha_g - X\beta). \quad (1)$$

Without loss of generality, an outcome with p levels may be coded using the first p integers, such that g may take on the values $1, \dots, p$. In the expression above, α_g is a scalar intercept, expit is the logistic (inverse logit) transformation, and the vector X contains coded baseline covariates and the active/placebo treatment indicator. The model has intercepts for each of the first $p - 1$ outcome levels, and the intercepts must be ordered: $\alpha_1 \leq \alpha_2 \leq \dots \leq \alpha_{p-1}$. The ordering of intercepts ensures that the probabilities $\Pr(G \leq g|X)$ are monotonically increasing in g . The parameter vector β represents the log odds ratios (OR) associated with the effects of covariates and group assignment. Specifically, the group assignment odds ratio represents the relative effect of treatment versus placebo on the odds $\Pr(G > g|X)/(1 - \Pr(G > g|X))$, for each of the first $p - 1$ values that G may take.

The $p - 1$ linear predictors $\alpha_g - X\beta$ represent the logit transformed cumulative probabilities associated with the first $p - 1$ levels of the ordinal outcome, adjusted for the effects of covariates X . The probabilities that the outcome takes a specific value g , adjusted for covariates X , is derived as follows:

$$\Pr(G = g|X) = \text{expit}(\alpha_g - X\beta) - \text{expit}(\alpha_{g-1} - X\beta), \quad (2)$$

where $\text{expit}(\alpha_0 - X\beta)$ and $\text{expit}(\alpha_p - X\beta)$ are defined to be 0 and 1, respectively.

When there are partially observed ordinal outcomes, it is convenient to recode the outcome as a vector $Y = [Y_1, \dots, Y_p]$, such that $Y_g = 1$ if $G = g$ or when g is one of the values that G might have taken if the outcome were fully observed, and $Y_g = 0$ otherwise. Thus, the cumulative logit model may be written as follows

$$\Pr(Y_1 = 1 \cup Y_2 = 1 \cup \dots \cup Y_g = 1|X) = \Pr(G \leq g|X) = \text{expit}(\alpha_g - X\beta). \quad (3)$$

Denote a sample of covariate vectors x_1, \dots, x_N and outcomes g_1, \dots, g_N , and corresponding outcome vectors y_1, \dots, y_N , where $y_i = [y_{i1}, \dots, y_{ip}]$. Using this representation, partially observed outcomes are encoded by assigning a value 1 to each element of y_i that the outcome g_i might have taken if fully observed. For example, if g_i might have taken values 1 or 2, but other values were not possible, then y_i would be coded $y_i = [1, 1, 0, \dots, 0]$. Further denote the collection of model parameters $\theta = [\alpha_1, \dots, \alpha_{p-1}, \beta]$. Using this notation, the observed data likelihood is as follows:

$$L(\theta|y_1 \dots y_N, x_1 \dots x_N) = \prod_{i=1}^N L_i(\theta|y_i, x_i) = \prod_{i=1}^N \sum_{j=1}^p I(y_{ij} = 1) \Pr(Y_j = 1|X = x_i), \quad (4)$$

where $I(\cdot)$ is the indicator function that takes a value 1 when its argument is true, and 0 otherwise.

In a Bayesian analysis, the posterior density function is proportional to the likelihood function multiplied by the prior density function as follows:

$$P(\theta|y_1 \dots y_N, x_1 \dots x_N) \propto L(\theta|y_1 \dots y_N, x_1 \dots x_N)P(\theta) \quad (5)$$

A flat prior distribution, where $P(\theta) \propto 1$, is used for all model parameters. Thus, the posterior density is proportional to the likelihood function.

Each supplemental estimand is a treatment difference in one of the following summaries of the adjusted outcome distribution: mean, median, proportion experiencing mortality by day 28, and proportion receiving oxygen every day until day 28. Supplemental estimands are computed using the probabilities expressed in equations (1) and (2) above, adjusted to the modal value for each covariate: age group 31-64, WHO COVID-19 Score value 4 (hospitalized receiving oxygen via nasal cannula), and male sex. The adjusted means are computed as the linear combination of all possible outcome values and their associated adjusted probabilities. The adjusted medians are computed as the smallest value of g such that the $\Pr(G \geq g|X) \geq 0.5$. The adjusted proportions of participants experiencing mortality by day 28 or oxygen requirement every day until day 28 are computed as $\Pr(G = -1|X)$ and $\Pr(G = 0|X)$, respectively.

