6.1 Statistical Model

The PO model can be written in terms of the covariates X and an outcome variable Y , where probabilities of outcome value y or greater $\Pr(Y \geq y|X) = \text{expit}(\alpha_y + X\beta)$ where α_y is the intercept for outcome value y and expit is the logistic (inverse logit) transformation and the columns of matrix X contain coded baseline covariates and the active/placebo treatment indicator. β represents the log odds ratio (OR) associated with the effects of covariates and group assignment. Specifically, the group assignment odds ratio represents the relative effect of treatment versus placebo on the odds $\Pr(Y \geq y|X)/(1 - \Pr(Y \geq y|X))$, for any value y .

A flat prior distribution will be used for all PO model parameters. This ensures that the estimate of the primary estimand will be free of influence from an informative prior, and the Bayesian maximum *a posteriori* estimate will be identical to the maximum likelihood estimate (see Appendix: Cumulative Logit Model). The posterior distribution for the log odds ratio will be approximated using the Laplace method.⁸ Use of a flat prior ensures the Laplace-approximated posterior distribution is identical to the asymptotic sampling distribution of the maximum likelihood estimate; in both cases a normal distribution centered at the estimate with variance-covariance equal to the negative inverse Hessian of the log likelihood function (inverse observed Fisher information; see Appendix: Laplace Approximation). All statistical inferences about the odds ratio will be made using this method. Statistical uncertainty about supplementary estimands (e.g., treatment difference in the median of the primary outcome) will be quantified using the delta method.⁹ Given the investigational nature of the agents tested by this platform, there is insufficient information upon which to justify a more informative prior. The flat prior approach ensures that Bayesian inferences regarding the efficacy of study agents are based exclusively on the data collected in the ACTIV 4 Host Tissue platform.

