6.6 Sample Size and Decision Thresholds

The maximum number of participants to be enrolled in sub studies under the Master Protocol is 600 participants per trial, resulting in approximately 300 patients per active treatment arm, and 300 patients in the matching placebo arm. The placebo arm will be shared across all active treatment arms. We expect placebo participants to continue to accrue for as long as there are additional treatments to test and cases to enroll.

Type-I error and power regarding the analysis of the primary outcome was assessed based on the pooled (across all active and placebo arms) distribution of the primary outcome among the first 100 participants to complete follow-up and monitoring. The efficacy threshold was identified using statistical simulation under the null hypothesis to ensure the study operating characteristics achieve design specifications. Pooled and blinded summaries of oxygen-free days at day 28 were used to approximate the distribution of the oxygen free days in the placebo group. Based on these data, the anticipated frequency distribution, mean, and median of oxygen-free days (OFDs) for the placebo group, and for the treatment group under hypothetical effect sizes computed using the PO model are displayed in the table below.

OFDs / Odds Ratio	Placebo	Inferiority		Superiority						
		0.67	0.80	1.40	1.45	1.50	1.55	1.60	1.65	1.70
Mean	8.8	6.6	7.5	10.8	11.1	11.3	11.5	11.7	11.9	12.0
Median	0	0	0	6.5	7.5	9.0	10.0	10.5	12.5	14.5
P(OFDs \geq 22)	0.19	0.14	0.16	0.25	0.26	0.26	0.27	0.28	0.29	0.29
Proportion:										
-1 (death)	0.235	0.316	0.279	0.181	0.176	0.171	0.166	0.162	0.158	0.154
0	0.296	0.314	0.309	0.268	0.264	0.261	0.257	0.254	0.251	0.247
1	0.006	0.006	0.006	0.006	0.006	0.006	0.006	0.006	0.006	0.006
---	---	---	---	---	---	---	---	---	---	---
27	0.050	0.034	0.041	0.069	0.072	0.074	0.076	0.078	0.081	0.083
28	0.000	0.000	0.000	0.000	0.000	0.000	0.000	0.000	0.000	0.000

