where H is the estimated Hessian, $\hat{\theta}$ is the MAP estimate, and Φ is the standard normal cumulative density function. This is implemented by the `clm_ppost` function for specified scalar elements θ_k . Notably, this function is used to compute the posterior probabilities used for decision-making at the interim and final analyses.

For supplementary estimands, $g(\theta)$, that are smooth scalar functions of θ (i.e., treatment difference in the mean of the primary outcome, and treatment difference in the probabilities associated with outcome categories -1 and 0), the posterior distribution will be approximated using the delta method, for example, to compute posterior cumulative probabilities as follows:

$$\Pr(g(\theta) \leq q|y_1 \dots y_N, x_1 \dots x_N) = \Phi \left(\frac{q - g(\hat{\theta})}{\sqrt{g'(\hat{\theta})^T [-H^{-1}] g'(\hat{\theta})}} \right),$$

Where $g'(\hat{\theta})$ is the gradient of $g(\cdot)$ evaluated at $\hat{\theta}$, which is approximated numerically using a finite difference method. For non-smooth scalar functions of θ (i.e., treatment difference in the median of the primary outcome), the posterior distribution will be identified using a Monte Carlo

method; by generating 10000 realizations from the posterior distribution for θ , and evaluating the supplementary estimand using those realizations. For either approach, an equal-tailed, level $(1 - \alpha)$ credible interval will then be identified by selecting the $\alpha/2$ and $1 - \alpha/2$ quantiles of the approximate posterior distribution. The functions `clm_crint_delta` and `clm_crint_montecarlo` compute credible intervals for supplementary estimands using the two methods described above, respectively. The adjusted outcome mean and median calculations are implemented by functions `mean_xp` and `quantile_xp`, respectively. The four supplementary estimands are implemented by functions defined in the R code file “supplemental_estimands.R”

The four supplementary estimands include the treatment difference in mean and median of the primary outcome, and the treatment difference in probabilities associated with outcome levels -1 and 0. Each of these estimands will be adjusted to the most common (modal) value for each covariate. The mean and median estimates are defined as the mean and median of the distribution defined by the cumulative probabilities associated with each outcome level, adjusted for covariates.

[figure not shown]

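### As printed, the SAP's adjusted-median rule always returns the lowest level (-1, death) in both groups, and the SAP names two different interval methods for the median difference

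*SAP*

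**What the plan says.** **The rule for the median.** SAP 11.1 (Model Formulation) begins "The adjusted medians are computed as the smallest value of" g and completes the rule with the condition Pr(G ≥ g|X) ≥ 0.5. The next sentence of that section writes day-28 mortality as Pr(G = -1|X), so g is on the oxygen-free-day scale, whose lowest value is -1.

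**Other descriptions of the same quantity.** SAP 11.3 takes it to be the "median of the distribution defined by the cumulative probabilities associated with each outcome level", adjusted for covariates, and names the function `quantile_xp`. Equation (1) in SAP 11.1, from which the supplementary estimands are to be computed, is in lower-tail form: "probabilities of outcome value g or smaller are modeled as follows". SAP 6.1 writes the same model in upper-tail form: "probabilities of outcome value y or greater". SAP 6.6 tabulates the "anticipated frequency distribution, mean, and median of oxygen-free days (OFDs) for the placebo group" and for a range of odds ratios; the medians there are 0 for placebo, 6.5 at OR 1.40 and 12.5 at OR 1.65.

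**The interval.** SAP 6.1 states: "Statistical uncertainty about supplementary estimands (e.g., treatment difference in the median of the primary outcome) will be quantified using the delta method". Protocol 8.5 has the same sentence. SAP 11.3 keeps the delta method for smooth functions, with a gradient "which is approximated numerically using a finite difference method". For functions that are not smooth it gives this instance and method: "treatment difference in the median of the primary outcome), the posterior distribution will be identified using a Monte Carlo" approach with 10000 posterior draws.

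**The age label.** SAP 11.1 sets the modal age group to 31-64; SAP 6 defines the model level as 31-65.

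**The concern.** SAP 6.4 gives the supplementary estimands the job of conveying the treatment effect to readers, and the median difference is one of only four. A SAP should let an independent statistician reproduce each of them from the text.

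Taken literally, the rule in 11.1 yields a median of death in each group and a difference of zero, for any data and any effect. A Monte Carlo interval built on it would also be zero at both ends, because every posterior draw gives -1 in both groups.

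The choice of interval method matters because the median of an integer outcome is a step function of the model parameters. The two methods named are not approximations of one another for such a function.

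**Working it through.** **1. The planning placebo median under the ordinary definition.** Inputs from the SAP 6.6 table: Pr(G = -1) = 0.235 and Pr(G = 0) = 0.296.

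- Pr(G ≤ -1) = 0.235, which is below 0.5.
- Pr(G ≤ 0) = 0.235 + 0.296 = 0.531, which is at least 0.5.

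The smallest g with Pr(G ≤ g) ≥ 0.5 is 0. This reproduces the tabulated placebo median.

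**2. The printed rule on the same distribution.**

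- Pr(G ≥ -1) = 1
- Pr(G ≥ 0) = 1 - 0.235 = 0.765
- Pr(G ≥ 1) = 1 - 0.531 = 0.469

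The values of g that satisfy Pr(G ≥ g) ≥ 0.5 are -1 and 0. The smallest is -1; the largest is 0, the ordinary median.

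**3. Across the planning scenarios,** using the tabulated proportions at -1 and 0:

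| Scenario | Pr(G ≤ 0) | Ordinary median | SAP 6.6 median | Printed rule |
|---|---|---|---|---|
| Placebo | 0.235 + 0.296 = 0.531 | 0 | 0 | -1 |
| OR 0.67 | 0.316 + 0.314 = 0.630 | 0 | 0 | -1 |
| OR 0.80 | 0.279 + 0.309 = 0.588 | 0 | 0 | -1 |
| OR 1.40 | 0.181 + 0.268 = 0.449 | above 0 | 6.5 | -1 |
| OR 1.65 | 0.158 + 0.251 = 0.409 | above 0 | 12.5 | -1 |

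The exact medians at OR 1.40 and 1.65 cannot be rebuilt, because the table omits levels 2 to 26.

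**4. In general.** Pr(G ≥ lowest level|X) = 1 for every covariate pattern and every odds ratio, so the printed rule returns the lowest level in both groups. Coding the levels 1 to p, or collapsing unobserved levels as 11.3 allows, changes only the label of that lowest level.

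**5. Two forms that work.** The smallest g with Pr(G ≤ g|X) ≥ 0.5 and the largest g with Pr(G ≥ g|X) ≥ 0.5 give the same value unless a cumulative probability is exactly 0.5. The word *smallest* belongs with the lower-tail form of equation (1). The upper-tail form of SAP 6.1 would need *largest*. The printed rule combines one half of each.

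**6. The delta method for a median.** Let m(θ) be the integer-valued median. A central difference with step h (assumed for illustration; the SAP states neither step nor type) is [m(θ + h) - m(θ - h)] / (2h).

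- If no jump lies within h of the estimate, the result is 0. When this holds for every parameter, the standard error is 0 and the interval has no width.
- If one jump of one day lies within h, the result has size 1/(2h): 500 at h = 0.001 and 50 at h = 0.01.

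The standard error is therefore either 0 or set by the step size. Monte Carlo draws from the posterior of θ avoid this.

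**The case against.** The strongest reply is that the SAP already answers the question. Section 11.1 says the estimands come from equations (1) and (2), and equation (1) is in lower-tail form. Section 11.3 states the ordinary median in words and names the function that computes it. On intervals, 6.1 is a general sentence with an example in brackets, while 11.3 separates smooth from non-smooth estimands, assigns the median by name, fixes the number of draws and names the Monte Carlo function. An analyst who reads 11.1 and 11.3 together would be unlikely to report -1 in both groups or use the delta method for the median.

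Most of this stands. It identifies the intended method, but it does not make the printed rule correct or remove the conflicting sentence in 6.1. Protocol 8.1 gives the SAP precedence over the protocol's statistical section, which settles Protocol 8.5 but not a conflict inside the SAP.

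Two further cautions also stand. The first part rests on one inequality sign in machine-read mathematics, which may be a misreading. The SAP 6.6 medians are supporting evidence only: they are not adjusted to modal covariates, and some are half-integers, which neither integer-valued rule can return, so they do not confirm the exact rule used in the code.

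A reader might infer that the trial will actually report a median of death in both groups. The documents do not support that: 11.3 points the other way and the code is not available.

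**Conclusion.** The point holds as a defect in the text. As printed in the available copy, the adjusted-median rule is degenerate and gives a difference of 0 whatever the effect. This is an identity and needs no assumption about the data. It contradicts 11.3 and does not fit equation (1). It is probably a one-symbol slip, subject to a check of the sign in the source document. The delta-method and Monte Carlo statements conflict regardless of that sign.

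The reach is narrow. Only the median difference, a descriptive supplementary estimand, is touched. A reader might infer that the efficacy conclusion or the design is weakened. It is not: the primary odds ratio, the 0.976 threshold, type-I error and power do not use the median, and the mean difference and the differences at levels -1 and 0 have their own formulas. The age mismatch (31-64 against 31-65) is a label error only, since the model uses category indicators.

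**What to change.** 1. Check the inequality sign in the source SAP. Define the adjusted median in 11.1 as the smallest g with Pr(G ≤ g|X) ≥ 0.5 (equivalently here, the largest g with Pr(G ≥ g|X) ≥ 0.5).
2. Confirm that `quantile_xp` does this.
3. Remove the median example from the delta-method sentence in SAP 6.1. Align Protocol 8.5, or note that the SAP supersedes it, so that the Monte Carlo method in 11.3 is the only one stated.
4. Clerical: change 31-64 in SAP 11.1 to 31-65.

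The cost is a few wording edits and one code check. No analysis is added, and the primary estimand, decision thresholds and sample size stay as they are.

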11.2 Model-based Statistical Inferences

The posterior distribution for the log odds ratio and any other required parameter is approximated using the Laplace method. A flat prior ensures the Laplace-approximated posterior distribution is identical to the approximate sampling distribution of the maximum likelihood estimate for θ ; in both cases a normal distribution centered at the estimate (i.e., the maximum likelihood estimate or equivalently the maximum *a posteriori* estimate) with variance-covariance equal to the negative inverse Hessian of the log likelihood function (inverse observed Fisher information) evaluated at the estimate (see “Appendix: Laplace Approximation”). All statistical inferences about the odds ratio and derivative quantities (including all supplementary estimands) will be made using this method.

11.3 Model Fitting and Computation

The cumulative logit model is implemented in the R code file “`clm_model.R`”. Readers should examine the `clm_fit` function first, which is the entry point for model fitting, and then examine other functions as they are called by `clm_fit`. The function `clm_fit` takes as arguments the matrix of coded covariates x , and a matrix of coded outcomes y . Each matrix has one row per record (i.e., study participant). The covariate matrix has one column per coded covariate (e.g., age group has three levels and thus requires two columns to distinguish the levels), and the outcome matrix has one column per value that the outcome might take. The cells of the outcome matrix y contain the values y_{ij} as defined above (see “Model Formulation”).

In practice, when one or more levels of an ordinal outcome are not observed in the analysis data set, some of the model intercepts are not estimable (i.e., there is no unique set of model intercepts that maximizes the likelihood/posterior density function). To overcome this, each outcome level is characterized as “estimable” if there is at least one record in the analysis data set where that level is observed and no other level was possible (i.e., ignoring partially observed outcomes), and “not estimable” otherwise. Levels of the outcome that are not estimable are collapsed with the nearest adjacent estimable level to form a new level, e.g., levels 3, 4, and 5 may be collapsed to form level “3|5”. When levels are collapsed, if any collapsed level was possible as part of a partially observed outcome, then the collapsed level is considered possible as well. This functionality is implemented by the function `clmCollapse`, which is called by `clm_fit` prior to any model fitting.

The estimate of θ is found by maximizing the log of the posterior density function (i.e., a maximum *a posteriori* estimate, or MAP for short) defined in expression (5). Note that the normalizing constant in expression (5) is not needed to identify the MAP estimate, nor is it necessary to form a Laplace approximation to the posterior density. The estimate of θ is found using an iterative optimization algorithm, and the associated observed Fisher information is estimated using a finite difference method. These calculations are implemented using the R function `optim`, which uses the quasi-Newton “BFGS” method (Byrd, Lu, Nocedal, and Zhu,

1995, A limited memory algorithm for bound constrained optimization. *SIAM Journal on Scientific Computing*, 16, 1190–1208. doi: 10.1137/0916069), and is built-in as part of the “stats” package for R (R Core Team, 2022, R: A language and environment for statistical computing. R Foundation for Statistical Computing, Vienna, Austria. URL <https://www.R-project.org/>). The initial values for β are set to zero. Initial values for the model intercepts are generated by first calculating the fraction of each observed outcome level (i.e., an initial estimate of $\Pr(G = g|X)$ where $\beta = 0$), and then applying the inverse of expression (2) as follows:

$$\alpha_g^{\text{init}} = \text{logit} \left(\sum_{k=1}^g \frac{\sum_i y_{ik}}{\sum_i \sum_j y_{ij}} \right). \quad (6)$$

The initial values calculations for the model intercepts are implemented by the function `clm_alpha_init`. Starting at the initial values, the `optim` function iteratively maximizes the `clm_optim` function, which computes the log of the posterior density function given by expression (5). The `clm_optim` function calls the `clm_loglik` and `clm_logpri` functions, which evaluate the log of the likelihood function given by expression (4) and log of the prior density function (defined to be zero for a flat prior), respectively. The `clm_loglik` function calls `clm_predict` which computes, for each record, the linear predictors, $\alpha_g - X\beta = \text{logit} \Pr(G \leq g|X)$, and the associated covariate adjusted probabilities for each ordinal outcome level $\Pr(G = g|X)$. The `clm_predict` function calls `alpchs_to_probs` to convert the logit cumulative probabilities to level specific probabilities according to expression (2). The `probs_to_alpchs` function computes the inverse of `alpchs_to_probs`.

The `clm_fit` function returns a model fit object that contains a model convergence assessment, the MAP estimate for θ , and the estimated Hessian of the log posterior density function evaluated at the estimate. The MAP estimate and Hessian are sufficient to define the Laplace (Normal) approximation to the posterior density, and are used to compute posterior cumulative probabilities as follows

$$\Pr(\theta_k \leq q|y_1 \dots y_N, x_1 \dots x_N) = \Phi \left(\frac{q - \hat{\theta}_k}{\sqrt{[-H^{-1}]_{kk}}} \right),$$

where H is the estimated Hessian, $\hat{\theta}$ is the MAP estimate, and Φ is the standard normal cumulative density function. This is implemented by the `clm_ppost` function for specified scalar elements θ_k . Notably, this function is used to compute the posterior probabilities used for decision-making at the interim and final analyses.

For supplementary estimands, $g(\theta)$, that are smooth scalar functions of θ (i.e., treatment difference in the mean of the primary outcome, and treatment difference in the probabilities associated with outcome categories -1 and 0), the posterior distribution will be approximated using the delta method, for example, to compute posterior cumulative probabilities as follows:

$$\Pr(g(\theta) \leq q|y_1 \dots y_N, x_1 \dots x_N) = \Phi \left(\frac{q - g(\hat{\theta})}{\sqrt{g'(\hat{\theta})^T [-H^{-1}] g'(\hat{\theta})}} \right),$$

Where $g'(\hat{\theta})$ is the gradient of $g(\cdot)$ evaluated at $\hat{\theta}$, which is approximated numerically using a finite difference method. For non-smooth scalar functions of θ (i.e., treatment difference in the median of the primary outcome), the posterior distribution will be identified using a Monte Carlo

method; by generating 10000 realizations from the posterior distribution for θ , and evaluating the supplementary estimand using those realizations. For either approach, an equal-tailed, level $(1 - \alpha)$ credible interval will then be identified by selecting the $\alpha/2$ and $1 - \alpha/2$ quantiles of the approximate posterior distribution. The functions `clm_crint_delta` and `clm_crint_montecarlo` compute credible intervals for supplementary estimands using the two methods described above, respectively. The adjusted outcome mean and median calculations are implemented by functions `mean_xp` and `quantile_xp`, respectively. The four supplementary estimands are implemented by functions defined in the R code file “supplemental_estimands.R”

The four supplementary estimands include the treatment difference in mean and median of the primary outcome, and the treatment difference in probabilities associated with outcome levels -1 and 0. Each of these estimands will be adjusted to the most common (modal) value for each covariate. The mean and median estimates are defined as the mean and median of the distribution defined by the cumulative probabilities associated with each outcome level, adjusted for covariates.

[figure not shown]
